#### **4. Study Treatments**

##### **4.1 Method of Assigning Subjects to Treatment Groups**

All subjects will be centrally assigned to randomized study intervention using interactive response technology (IRT). Before the study is initiated, the log-in information and directions for the IRT will be provided to qualified personnel at each site.

All qualified subjects will be assigned to receive AR-15512 vehicle BID to both eyes for approximately 14 days during the vehicle run-in period. Following the run-in period, all subjects who requalify at Baseline (Day 1) will be randomized in a 1:1 ratio, within each site, to receive 0.003% AR-15512 or AR-15512 vehicle. The IRT will provide the site with the specific kit number(s) for each randomized subject at the time of randomization. Sites will dispense the study intervention according to the IRT instructions and the Schedule of Visits and Assessments as in Table 1.

Individuals who do not meet the criteria for participation in this study (screen failures) may be rescreened for eligibility up to one time if there is reasonable possibility, in the Investigator's opinion, that the patient might meet the eligibility criteria. When a subject is rescreened, a new subject ID will be assigned, and the previous subject id will be recorded in the Informed Consent CRF form.

The subject ID will be in the format of xxx-xxx, with the first 3 characters being the site number and the last 3 characters sequentially numbered starting from 001 within the site, which will be used to identify subjects in all datasets and listings for this study.

##### **4.2 Masking and Unmasking**

###### **4.2.1 MASKING**

During the vehicle run-in period, the subject will be masked. During the randomized study intervention period, the Investigator and site staff performing eligibility/efficacy and safety assessments and the subjects will be masked. Subjects will remain masked during the randomized phase. Subjects will be informed that they all will receive vehicle at some point in the study, but the exact timing will not be specified. AR-15512 (0.003%) and AR-15512 vehicle will be provided in identical single-use blow-fill-seal containers.

###### **4.2.2 UNMASKING**

A randomization schedule for allocating the study interventions within a site will be prepared by an unmasked statistician who is not involved in the day-to-day conduct of the study.

Study intervention assignments will be masked to the Investigator, the clinical study team (Sponsor, personnel involved in day-to-day study management, Monitors, Data Managers, and Statisticians), and the subjects. Only in case of medical emergency or occurrence of AEs that warrant unmasking in the opinion of the Investigator, will the study intervention assignment(s) be unmasked and made available to the

Investigator and the Medical Monitor. In the absence of medical need, the randomization code will not be available to the above personnel until after the study is completed and the database is locked.

If the Investigator feels it is necessary to unmask a subject's study intervention assignment after an emergency situation, the Investigator should contact the Medical Monitor or designee. Only after consultation with the Medical Monitor will a decision be made as to whether or not the study intervention for the subject should be unmasked. The study intervention assignment will be revealed on a subject-by-subject basis, thus leaving the masking on the remaining subjects intact.

## **5. Sample Size and Power Considerations**

Two hundred two (202) ITT population subjects (study eyes) per treatment group yields 99% power to conclude superiority of 0.003% AR-15512 over vehicle in the proportion of subjects with  $\geq 10$  mm increase in unanesthetized Schirmer score on Day 14, assuming a true difference of proportions (AR-15512 vs vehicle) of 80% vs 30% and a two-sided alpha=0.05.

Additionally, 202 ITT population subjects (study eyes) per treatment group yields 99% power to conclude superiority of 0.003% AR-15512 over vehicle in the mean change from baseline in SANDE score on Day 28 assuming a true difference (AR-15512 minus vehicle) of -8.3, a common standard deviation (SD) of 17.72, and a two-sided alpha=0.05.

Accounting for subject discontinuations, approximately 460 total subjects (230 per treatment arm) will be randomized assuming a dropout rate of 10%.

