**Efficacy Assessments:**

Primary Assessments:

- Unanesthetized Schirmer test

Secondary Assessments:

- SANDE (Symptom Assessment iN Dry Eye) Questionnaire Score
- Ocular Discomfort Score (ODS) - Visual Analog Scale (VAS)
- Eye Dryness Score based - VAS

Safety Assessments:
 

• Vital signs (heart rate and blood pressure)

• Hematology, chemistry, and urinalysis

• Adverse events

• Corrected visual acuity

• Intraocular pressure

• Dilated fundus exam

Statistical Methods:
 
Sample Size Determination
 
Two hundred two (202) intention-to-treat (ITT) population subjects (study eyes) per treatment group yields 99% power to conclude superiority of 0.003% AR-15512 over vehicle in the proportion of subjects <math>\geq 10</math> mm in unanesthetized Schirmer score on Day 14, assuming a true difference of proportions (AR-15512 vs vehicle) of 80% vs 30% and a two-sided alpha = 0.05.
 
Additionally, 202 ITT population subjects (study eyes) per treatment group yields 99% power to conclude superiority of 0.003% AR-15512 over vehicle in the mean change from Baseline in SANDE score on Day 28 assuming a true difference (AR-15512 minus vehicle) of -7.9, a common standard deviation of 17.72, and a two-sided alpha = 0.05.
 
Accounting for subject discontinuations, approximately 460 total subjects (230 per treatment arm) will be randomized assuming a dropout rate of 10%.

Primary endpoint
 

• Proportion of subjects <math>\geq 10</math> mm increase in unanesthetized Schirmer score on Day 14

Secondary endpoints
 

• Change from Baseline in SANDE score on Day 28

• Change from Baseline in unanesthetized Schirmer score on Day 14

• Change from Baseline in SANDE Score on Day 90
 
• Change from Baseline in ODS - VAS on Day 90
 
• Change from Baseline in Eye Dryness - VAS Day 90

- Proportion of subjects  $\geq 10$  mm increase in unanesthetized Schirmer score on Day 90
- Change from Baseline in unanesthetized Schirmer score on Day 90

Statistical Analyses

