### **4.1 Study Population**

This study is anticipated to enroll approximately 460 subjects with DED as defined below in Sections 4.2 and [4.3](#) so as approximately 414 subjects complete Day 90. The anticipated dropout rate is 10%. To achieve this goal, approximately 1500 subjects may be screened.

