## **9.2 Determination of Sample Size**

Two hundred two (202) ITT population subjects (study eyes) per treatment group yields 99% power to conclude superiority of 0.003% AR-15512 over vehicle in the proportion of subjects with  $\geq 10$  mm increase in unanesthetized Schirmer score on Day 14, assuming a true difference of proportions (AR-15512 vs vehicle) of 80% vs 30% and a two-sided alpha = 0.05.

Additionally, 202 ITT population subjects (study eyes) per treatment group yields 99% power to conclude superiority of 0.003% AR-15512 over vehicle in the mean change from Baseline in SANDE score on Day 28 assuming a true difference (AR-15512 minus vehicle) of -7.9, a common SD of 17.72, and a two-sided alpha = 0.05.

Accounting for subject discontinuations, approximately 460 total subjects (230 per treatment arm) will be randomized assuming a dropout rate of 10%.

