## **7. Analysis Populations**

### **7.1 Intent-to-Treat**

The Intent-to-Treat (ITT) population includes all randomized subjects. The primary efficacy analysis will be performed on the ITT population. Subjects in the ITT will be analyzed as randomized.

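### Do the differing SANDE effects (-7.9 in the protocol, -8.3 in the SAP) and the 202 per arm labelled ITT undermine the sample-size basis?

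*SAP*

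**What the plan says.** SAP section 5 assumes, for the SANDE secondary endpoint, "SANDE score on Day 28 assuming a true difference (AR-15512 minus vehicle) of -8.3", with "a common standard deviation (SD) of 17.72, and a two-sided alpha=0.05". Protocol section 9.2 has the same sentence with a different effect, "SANDE score on Day 28 assuming a true difference (AR-15512 minus vehicle) of -7.9", and the same remaining inputs, "a common SD of 17.72, and a two-sided alpha = 0.05". The protocol synopsis agrees with section 9.2: "of -7.9, a common standard deviation of 17.72, and a two-sided alpha = 0.05".

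Both documents say that 202 ITT subjects per arm give 99% power for SANDE on Day 28. They say the same for the primary endpoint, the proportion gaining at least 10 mm on the unanesthetized Schirmer test at Day 14, assumed to be 80% vs 30%.

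On enrolment, SAP section 5 plans "approximately 460 total subjects (230 per treatment arm) will be randomized assuming a dropout rate of 10" per cent. Protocol section 4.1 sets the total "so as approximately 414 subjects complete Day 90". SAP section 7.1 defines the analysis set: "The Intent-to-Treat (ITT) population includes all randomized subjects". SAP sections 2.3.1 and 8.3.1 handle missing data by multiple imputation, and section 13.5 carries that over to SANDE.

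**The concern.** Three things look wrong side by side.

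- **The effect.** It grows by 0.4 points (0.4/7.9 = 5%) between protocol and SAP, while the standard deviation, sample size and power stay put. That looks like one input edited and nothing recalculated.
- **The label.** If ITT is everyone randomised and missing values are imputed, the ITT count is 230 per arm, not 202.
- **The dropout arithmetic.** If 202 means completers, 10% loss from 230 gives 207. Read literally, 202 of 230 is a 12.2% loss, and 202 inflated for 10% dropout gives 225 rather than 230.

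If any of this hid a shortfall, the trial could be underpowered for the SANDE endpoint, the first-listed secondary and the more demanding of the two powered comparisons. Short of that, the study report would inherit two versions of the design basis.

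**Working it through.** **Inputs.** SANDE difference -7.9 (protocol synopsis and 9.2) or -8.3 (SAP 5); SD 17.72; two-sided alpha 0.05; 1:1 allocation; 202 per arm; primary response rates 80% and 30%; about 230 per arm randomised; 10% dropout; about 414 completers.

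**Step 1: reproduce the stated SANDE power.** Power ≈ Φ(|δ|/SE − 1.960), with SE = SD × √(2/n).

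At n = 202, SE = 17.72 × √(2/202) = 1.763.

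- δ = -7.9: 7.9/1.763 = 4.480; less 1.960 is 2.521; power 99.4%.
- δ = -8.3: 8.3/1.763 = 4.707; less 1.960 is 2.747; power 99.7%.

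The noncentral t gives the same values (99.4% and 99.7%). The stated 99% is therefore met under both effects.

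**Step 2: is 202 the minimum for 99%?** n = 2 × [17.72 × (1.960 + 2.326)/δ]².

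- δ = -7.9: 184.9, so 185 per arm (186 by t).
- δ = -8.3: 167.5, so 168 per arm (169 by t).

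Neither is 202. But the documents say what 202 delivers, not that it is the smallest adequate number. The effect that would give exactly 99% at 202 is about 7.56 by the normal formula, smaller than either assumption.

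**Step 3: primary endpoint.** Null SE = √(2 × 0.55 × 0.45/202) = 0.0495. Alternative SE = √((0.8 × 0.2 + 0.3 × 0.7)/202) = 0.0428. (0.50 − 1.960 × 0.0495)/0.0428 = 9.4, so power is above 99.99%. About 32 per arm would give 99%.

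**Step 4: dropout.** 230 × 0.9 = 207 per arm, or 414 in total, which matches protocol 4.1 and exceeds 202. In the other direction, 202/0.9 = 224.4, so 225 per arm (450 in total), against an approximate 230 (460). The gap is 5 per arm and lies on the side of more subjects.

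**Step 5: power at the other candidate numbers** (same formula).

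| n per arm | -7.9 | -8.3 |
|---|---|---|
| 202 | 99.4% | 99.7% |
| 207 | 99.5% | 99.7% |
| 230 | 99.8% | 99.9% |

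**Step 6: should the documents quote the 230 row, since ITT is imputed?** No. Imputed values do not carry full information, so with 10% missing at random the power is roughly that of 207 per arm. In addition, SAP 2.3.1 imputes withdrawals for lack of efficacy, adverse events or disallowed treatment from the vehicle arm, which can shrink the effect.

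As an extreme assumption, let all 10% of active-arm subjects be imputed that way, so that the effect is multiplied by 0.9 (to 7.11 or 7.47).

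- SE at n = 230 (1.652): power 99.0% or 99.5%.
- SE at n = 207 (1.742): power 98.3% or 99.0%.

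This overstates the loss. The 10% is dropout through Day 90, SANDE is tested at Day 28, and only some withdrawals fall in those categories. It does show that 99% is a fairer summary than 99.8% or 99.9%.

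**The case for a change.** The strongest case for acting is that the discrepancy is plain and cheap to mend. The SAP names the current protocol version as its basis, so -7.9 is not superseded text. The SAP's precedence over the protocol's statistical methods does not explain why a design assumption moved. The 202 cannot be the ITT count as both documents define it. And since losses by Day 14 or Day 28 cannot exceed losses by Day 90, the evaluable number at those visits should be at least 207. Two sentences would put it right.

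The two factual points stand: the effects differ, and 202 is better described as evaluable subjects.

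The stronger claims do not. The stated power is not wrong, because it is met under both effects. The 202 does not conflict with 10% dropout, because a required number may sit below the expected 207 and the enrolment figures are given as approximate. Nor can it be said that SANDE set the 202, since SANDE needs at most 186 for 99%. Whether the change of effect is unexplained cannot be settled from the public text: the Phase 2b results are redacted, and the clarification letters that the SAP relies on are not included.

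**Conclusion.** No change to the plan follows. The SANDE effect is inconsistent by 0.4 points and the 202 carries the wrong population label; both are clerical. Power at 202 per arm is 99.4% or 99.7% for SANDE and above 99.99% for the primary, so the 99% claim survives whichever effect was intended. The 207 per arm left after 10% dropout exceeds 202. Enrolment, endpoints, analysis and significance level are the same under either reading.

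This rests on the stated SD of 17.72, equal allocation, and a two-sample comparison without credit for the baseline and centre terms in the ANCOVA. It also takes dropout to be no worse than 10%. Vehicle-based imputation could trim SANDE power, to 98.3% in the extreme case shown, which is still ample. If the sample-size paragraph is reopened for another reason, one effect, an evaluable label for the 202 and power given as at least 99% would tidy it. Quoting 99.8% or 99.9% at 230 per arm would overstate what the imputed analysis delivers.

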## **6. Data Preparation**

### **6.1 Input Data**

Study data will primarily be recorded on the electronic Case Report Forms (eCRFs) supplied by Statistics & Data Corporation (SDC) using electronic data capture (EDC) system, Medidata RAVE. In addition, the following study data which is not captured directly within the EDC system but is obtained from external vendors will also be included for analysis. These data sources are described in detail in data transfer agreements developed between data management and the respective external laboratory:

- Central laboratory data from ACM Global Laboratories (hematology, chemistry, and urinalysis)

When all prerequisites for database lock have been met, including availability of all masked external data, the database will be locked. Following database lock, approval will be obtained from the Sponsor to unmask the study. Any changes to the database after data have been locked can only be made with the approval of the Sponsor in consultation with SDC.

Final analysis will be carried out after the following have occurred:

- Database lock has occurred, including receipt of all final versions of external vendor data, with written authorization provided by appropriate SDC and Sponsor personnel.
- Protocol deviations have been identified and status defined (major/minor deviations).
- Analysis populations have been determined.
- Randomized treatment codes have been unmasked.

## **6.2 Output Data**

Data from EDC and external data will be transferred to SDC Biostatistics and incorporated into standard formats following the Study Data Tabulation Model (SDTM). Data will then be mapped to analysis datasets using the Analysis Data Model (ADaM). Both SDTM- and ADaM-formatted data will be used to create the subject listings, while all tables and figures will be based on the ADaM-formatted data.

SDTM will follow the SDTM version 1.7 model and will be implemented using the SDTM Implementation Guide version 3.3 and the most recent SDTM Controlled Terminology version at the time of programming start. ADaM data will follow the ADaM version 2.1 model and will be implemented using the ADaM Implementation Guide version 1.1. Both SDTM and ADaM will be validated using Pinnacle 21 version 4.0.0 or above. Any discrepancies in the validation will be noted in reviewer's guides accompanying the final data transfers. The actual versions will be determined at the time of programming start. Define.xml will be created for SDTM and ADaM using the Define-XML version 2.0 model or above.

## **7. Analysis Populations**

### **7.1 Intent-to-Treat**

The Intent-to-Treat (ITT) population includes all randomized subjects. The primary efficacy analysis will be performed on the ITT population. Subjects in the ITT will be analyzed as randomized.

### **7.2 Per Protocol**

The Per Protocol (PP) population includes subjects in the ITT population who do not have significant protocol deviations likely to seriously affect the primary outcome of the study and who complete the trial through Day 28. Protocol deviations will be assessed prior to database lock and unmasking. The PP population will be analyzed using observed data only for efficacy variables. Subjects in the PP population will be analyzed as treated.

### **7.3 Safety**

The Safety population includes all randomized subjects who have received at least one dose of the investigational product. The Safety population will be analyzed for all safety assessments. Subjects in the Safety population will be analyzed as treated.

## 8. General Statistical Considerations

### 8.1 Unit of Analysis

Safety endpoints will be analyzed for both eyes. For efficacy endpoints assessed at the eye level, the unit of analysis will be the “study eye” as defined in [Section 8.2](#). For efficacy endpoints assessed in both eyes (OU), the unit of analysis will be the subject.

### 8.2 Study Eye Selection

The study subject must have at least one eye (the same eye) meeting all the inclusion criteria and none of the exclusion criteria at both Screening and Baseline (Day 1) visits where applicable. Study subjects will be dosed in both eyes. If both eyes are eligible at the time of randomization, the study eye will be defined as the eye with the lower pre-drop unanesthetized Schirmer score at the Baseline (Day 1) visit. If both eyes still qualify and have the same pre-drop unanesthetized Schirmer score, the right eye (OD) will be designated as the study eye.

Study eye will not be directly collected in EDC. Instead “Qualifying Eye” will be collected at Baseline (Day 1) visit. When one eye is the qualifying eye, then it will be the study eye. If both eyes are qualified, then study eye will be derived programmatically based on study eye selection criteria in this section. The non-study eye will be referred to as the fellow eye.

### 8.3 Missing or Inconclusive Data Handling

#### 8.3.1 MISSING EFFICACY ASSESSMENTS

The primary analysis will be based on MI methodology as specified in Estimand 1 ([Section 2.3.1](#))

#### 8.4 Definition of Baseline

Baseline is defined as the last non-missing measure prior to the initiation of randomized study intervention.

- The efficacy endpoint baseline will be the Baseline (Day 1) measurement. Screening visit and unscheduled visit measurements if any prior to the initiation of randomized study intervention **will not be considered** for baseline even when Baseline (Day 1) measurement is missing.
- For unanesthetized Schirmer test measures taken at both pre-drop and post-drop, the pre-drop measure at Baseline (Day 1) will be the baseline for primary and secondary analyses as specified

in Sections 2.1.1 and 2.1.2, [REDACTED]  
[REDACTED]

- The safety endpoint baseline will be the Baseline (Day 1) measurement. When Baseline (Day 1) measurement is missing, the last non-missing measurement from Screening visit and unscheduled visit measurements prior to the initiation of randomized study intervention **will be considered** for baseline.

## 8.5 Data Analysis Conventions

All data analysis will be performed by SDC. Statistical programming and analyses will be performed using SAS® Version 9.4 or higher. Output will be provided in rich text format (RTF) for tables and portable document format (PDF) for tables, listings, and figures using landscape orientation.

Summaries for continuous and ordinal variables will include the number of observations (n), arithmetic mean, SD, median, minimum, and maximum. Minima and maxima will be reported with the same precision as the raw values; means and medians will be presented to one additional decimal place than reported in the raw values. Standard deviations will be presented to two additional decimal places than reported in the raw values. Summaries for discrete variables will include counts and percentages. All percentages will be rounded to one decimal place (i.e., XX.X%). Change from baseline will be calculated as, Post-Baseline Result – Baseline, and treatment comparisons will be calculated as, AR-15512 (0.003%) – Vehicle.

All statistical tests will be two-sided with a significance level of 0.05 ( $\alpha=0.05$ ) unless otherwise specified. Confidence intervals (CIs) for differences between treatment groups will be two-sided at 95% confidence. All p-values will be rounded to 4 decimal places; p-values less than 0.0001 will be presented as “<0.0001”; p-values greater than 0.9999 will be presented as “>0.9999.”

Unless otherwise specified, summaries will be presented by treatment group and, where appropriate, visit. Listings will be presented by treatment group, subject number, visit/time point, and parameter as applicable using all randomized subjects. Early termination visit (ET) and unscheduled visits will not be summarized in table summaries and will only be presented in listings.

[REDACTED]

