**Table 3      Study Intervention Dispensing Schedule**

Study Day	Quantity Dispensed to Subject
-14	1 Run-In kit (40 vials)
1	1 Randomized Intervention Kit (40 vials)
7	1 vial administered in-office from the Day 7 Kit
14	1 Randomized Intervention Kit (40 vials)
28	2 Randomized Intervention Kits (80 vials)
60 	2 Randomized Intervention Kits (80 vials)
90	Study Exit

[figure not shown]
1. Dispensation and collection of study intervention only. No other procedures are scheduled on this day.

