#### **14.2 Clinical Laboratory Data**

Clinical laboratory data including hematology, coagulation, and urinalysis will be collected at Baseline (Day 1), and Day 90 or ET. Overall clinical laboratory results at each visit will be reviewed and be interpreted as normal, abnormal, NCS (non-clinically significant), and abnormal, CS (clinically significant). Abnormal, CS results will be specified.

The actual and change from baseline in laboratory test results will be summarized using continuous descriptive statistics for each treatment group. The interpretation of results relative to the reference range (low panic, low normal, normal, high normal, high panic, abnormal) will be summarized using counts and percentages for each treatment group. Shift tables for the interpretation of results relative to the reference range will be provided comparing baseline with Day 90.

Subject listings of laboratory results (hematology, coagulation, and urinalysis) will be produced. When deemed necessary, manual differential results may be collected, which will be listed in the subject listing for hematology. Urine microscopic results may be collected when abnormal urinalysis results are observed, which will be listed in the subject listing for urinalysis. In addition, the overall laboratory results review and interpretation at each visit will be presented in a separate listing.

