#### **14.3 Vital Signs**

Vital signs (sitting heart rate in beats/min and sitting blood pressure in mmHg [systolic and diastolic blood pressure]) will be assessed at Screening, Baseline (Day 1), and Day 90 or ET.

The actual and change from baseline in vital signs will be summarized using continuous descriptive statistics by visit for each treatment group. A subject listing of visual acuity will be produced.

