#### **14.6 Intraocular Pressure**

Intraocular pressure will be assessed in both eyes at Screening, Baseline (Day 1), Day 90 and ET by a Goldmann applanation tonometer affixed to a slit lamp as preferred device. Results will be taken from a single measurement and will be recorded in mmHg.

The IOP values and changes from baseline for each eye (study eye and fellow eye) will be summarized using continuous descriptive statistics by visit and for each treatment group. A subject listing of IOP will also be produced.

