#### **14.7 Dilated Fundus Exam**

Dilated fundus exam of vitreous, retina, macula, optic nerve, and choroid will be performed at Screening, Baseline (Day 1), and Day 90 or ET. The results will be graded as normal, abnormal NCS, or abnormal CS.

Shift tables for the dilated fundoscopy parameters will also be provided comparing each follow-up visit to baseline by region, finding, and eye (study eye and fellow eye). A subject listing of the dilated fundoscopy parameters will also be produced.

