Table 14.3.2.2.3	Urinalysis Results by Visit	Safety Population
Table 14.3.2.3.1	Shift in Hematology from Baseline to Day 90	Safety Population
Table 14.3.2.3.2	Shift in Chemistry from Baseline to Day 90	Safety Population

Table Number	Title	Population
Table 14.3.2.3.3	Shift in Urinalysis from Baseline to Day 90	Safety Population
Table 14.3.3	Actual and Change from Baseline in Vital Signs by Visit	Safety Population
Table 14.3.4.1	Actual and Change from Baseline in Corrected Visual Acuity in logMAR Score by Visit	Safety Population
Table 14.3.4.2	Categorical Analysis of Change from Baseline in Corrected Visual Acuity logMAR Score by Visit	Safety Population
Table 14.3.5.1	Shift in Slit-Lamp Biomicroscopy Results by Visit – Study Eye	Safety Population
Table 14.3.5.2	Shift in Slit-Lamp Biomicroscopy Results by Visit – Fellow Eye	Safety Population
Table 14.3.6	Actual and Change from Baseline in Intraocular Pressure (mmHg) by Visit	Safety Population
Table 14.3.7.1	Shift from Baseline in Dilated Fundus Exam Results to Day 90 – Study Eye	Safety Population
Table 14.3.7.2	Shift from Baseline in Dilated Fundus Exam Results to Day 90 – Fellow Eye	Safety Population

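### SAP 8.5 sends early termination values to listings only, so the post-baseline tables for laboratory tests, vital signs, IOP and fundus cover only subjects who attend Day 90

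*SAP*

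**What the plan says.** The general rule is in SAP 8.5: "Early termination visit (ET) and unscheduled visits will not be summarized in table summaries and will only be presented in listings". The text just after it is redacted, and the visible numbering goes from 8.5 to 8.7.

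The four assessments concerned are scheduled as follows.

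- **Laboratory tests** (SAP 14.2): data "will be collected at Baseline (Day 1), and Day 90 or ET". For the shifts, "Shift tables for the interpretation of results relative to the reference range will be provided comparing baseline with Day 90".
- **Vital signs** (SAP 14.3): these "will be assessed at Screening, Baseline (Day 1), and Day 90 or ET".
- **IOP** (SAP 14.6): "Intraocular pressure will be assessed in both eyes at Screening, Baseline (Day 1), Day 90 and ET".
- **Dilated fundus exam** (SAP 14.7): measured at the same times as vital signs. "Shift tables for the dilated fundoscopy parameters will also be provided comparing each follow-up visit to baseline", but the titles in SAP 19 read "Shift from Baseline in Dilated Fundus Exam Results to Day 90".

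Protocol Appendix 1 gives the same schedule. The only other visit between Day 28 and Day 90 is Day 60, of which the footnote to Protocol Table 3 says "No other procedures are scheduled on this day", beyond dispensing and collecting study intervention.

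SAP 7.3 defines the Safety population as everyone randomized and dosed, and SAP 14 applies it to all safety analyses. Protocol 7.3 includes all four assessments in the ET visit, on a best-effort basis. Protocol 6.10.1 asks sites to try for a final visit from subjects who withdraw consent or are discontinued for non-compliance.

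**The concern.** A table headed Safety population suggests that it describes post-baseline safety in everyone who was dosed. For these four assessments, the visible rules give a post-baseline picture of Day 90 attenders only. Protocol 6.10 lists adverse events among the reasons for leaving, so early leavers may differ from those who stay. Their ET measurements are requested by the protocol and then left out of every by-arm summary.

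The SAP already treats safety data more generously at the other end of follow-up. Section 8.4 lets a screening or unscheduled value stand in for a missing safety baseline and forbids this for efficacy. No visible post-baseline rule does the same.

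There is a smaller problem of the same kind in SAP 14.4. It builds the worst visual acuity value from scheduled and unscheduled visits, while 8.5 keeps unscheduled visits out of table summaries. It also leaves the status of ET values unclear. ET is not in the list of scheduled visits under Figure 1 of the SAP, and it is not unscheduled in the sense of Protocol 7.4, because the protocol specifies it.

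**Working it through.** **Step 1: apply 8.5 to each schedule.**

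| Assessment | Scheduled post-baseline times | Left after 8.5 | Visible tables (SAP 19) |
|---|---|---|---|
| Laboratory tests | Day 90, ET | Day 90 | 14.3.2.1 and 14.3.2.2 series by visit; 14.3.2.3 series shift to Day 90 |
| Vital signs | Day 90, ET | Day 90 | 14.3.3 by visit |
| IOP | Day 90, ET | Day 90 | 14.3.6 by visit |
| Dilated fundus exam | Day 90, ET | Day 90 | 14.3.7.1 and 14.3.7.2 shift to Day 90 |

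The pairing of Day 90 with ET in SAP 14.2, 14.3 and 14.7 says when data are collected. No visible sentence puts an ET value into a Day 90 row. The fundus text promises shifts for each follow-up visit, but Day 90 is the only such visit left. Visual acuity and slit-lamp examination also have Day 7, 14 and 28 rows, so the main point does not extend to them.

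**Step 2: reproduce the plan's figure.** Inputs are 460 randomized (230 per arm) and 10% dropout (SAP 5; Protocol 4.1 and 9.2).

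Expected at Day 90 = 460 × (1 − 0.10) = 414, which matches Protocol 4.1.

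**Step 3: subjects absent from the rows.**

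- At 10% dropout: 460 − 414 = 46, or 46/2 = 23 per arm. Coverage is 414/460 = 90.0%.
- At 5% dropout: 460 × 0.95 = 437, so 23 are absent, or 11.5 per arm. Coverage is 95.0%. The 5% is the Protocol 9.1.3 threshold for choosing a missing-data method, used here only as a lower reference point.

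**Step 4: how many could be recovered.** The documents give no ET attendance rate. Full attendance is unrealistic, because the visit is best-effort and subjects may leave through loss to follow-up, withdrawn consent or death. Attendance of 25%, 50% and 75% is therefore assumed.

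Recovered = absent × attendance; coverage = (Day 90 attenders + recovered)/460.

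| Dropout | Attendance | Recovered | Coverage |
|---|---|---|---|
| 10% | 25% | 46 × 0.25 = 11.5 | 425.5/460 = 92.5% |
| 10% | 50% | 46 × 0.50 = 23 | 437/460 = 95.0% |
| 10% | 75% | 46 × 0.75 = 34.5 | 448.5/460 = 97.5% |
| 5% | 25% | 23 × 0.25 = 5.75 | 442.75/460 = 96.25% |
| 5% | 50% | 23 × 0.50 = 11.5 | 448.5/460 = 97.5% |
| 5% | 75% | 23 × 0.75 = 17.25 | 454.25/460 = 98.75% |

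These counts use randomized subjects. The tables use dosed subjects, and the two should be close because site staff give the first randomized dose at the Day 1 visit (Protocol 5.2).

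**The case against.** The strongest reply is that 8.5 is a deliberate convention that can be programmed, and that the laboratory shift text and table titles agree with it. On that view, an extra row is a preference. It is true that the rule is clear for these four assessments and that nothing here is a transcription error. The point is that a better rule is available from data already collected.

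A second reply is that redacted text may already map ET values. That cannot be excluded. Such a rule would have to override the visible sentence in 8.5, so a cross-reference there would still be needed.

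A third is that early leavers are covered elsewhere, and much of this stands. ET values are listed by treatment group. Reasons for discontinuation are tabulated by arm (SAP 9), as are TEAEs leading to discontinuation of study intervention (SAP 14.1). Clinically significant laboratory changes at exit become AEs (Protocol 6.9.7). Continuous summaries show n, so the shortfall would be visible. A subject who stops treatment but attends Day 90 is already in the row. None of this, however, gives a by-arm summary of the routine ET measurements.

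Finally, a combined row mixes exposure durations and may include values taken after the last dose, because Appendix 1 sets no ET window. That is a real drawback, and it is why the Day 90 row should stay as it is.

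**Conclusion.** The point holds on the visible text. For laboratory tests, vital signs, IOP and the dilated fundus exam, the post-baseline, change and shift rows describe Day 90 attenders, not the whole Safety population named on the tables. At the planned dropout about 46 of 460 subjects are missing from them. The number recoverable depends on ET attendance, for which only an assumed range can be given.

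This is a matter of descriptive completeness. The documents give no rate of dropout due to AEs, so no direction or size of bias is claimed, and efficacy inference is untouched. The conclusion also rests on there being no ET mapping in the redacted parts. It is a modest improvement worth making because it costs little. Confidence is medium because of the redactions.

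**What to change.** In SAP 8.5, exempt these four assessments from the ET exclusion. Keep the Day 90 row unchanged and add a row and shift labelled *last on-study value (Day 90 or ET)*, with n per arm. Footnote that exposure durations differ, and give the interval from last dose to the ET visit, using the last-dose date that SAP 12.2 already relies on. If a redacted section already maps ET values into these tables, replace this with a cross-reference in 8.5.

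Separately, reconcile SAP 14.4 with 8.5 on unscheduled visits, and state whether ET values count towards worst visual acuity. Protocol 9.6 plans worst-value summaries for ocular safety assessments, which the visible SAP carries out only for visual acuity. If they are restored for other ocular assessments, label them *worst post-baseline*, or restrict them by date of last dose before calling them on-treatment.

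The cost is SAP wording and a few table shells, with no new data. The remaining downside is the mixed exposure and possible off-treatment values in the added row, which the footnote discloses.
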